### **Final Analysis Plan**

**The primary objective:** The primary objective of this study is to evaluate the time to recurrence (TTR) among three possible treatment groups, i.e., open surgery, endoscopic dilation, and endoscopic resection.

**Data analysis plan for the primary endpoint:** Demographic information will be tabulated. Descriptive statistics, including means, standard deviations, and ranges for continuous parameters, as well as percents and frequencies for categorical parameters, will be presented. For the primary objective analysis, i.e., estimating the TTR with 95% confidence interval, the TTR time will be estimated using the Kaplan-Meier method with the 95% confidence interval (CI). The Rothman CI, CI's based on Greenwoods variance, Thomas and Grunkemeier CI and the simultaneous confidence bands by Nair and Hall and Wellner will be reported. The logrank test will be used to compare the equality of survival curves. The generalized Wilcoxon and log-likelihood tests will also be examined, as these tests weight the survival function differently from the logrank test, which gives more weight to later occurring events. The Cox proportional hazards model will be applied to investigate potential prognostic factors, such as age on the TTR data. The adjusted p-values as well as the adjusted 95% confidence intervals from the Cox model will be reported. The adjusted hazard ratios and 95% CIs will be reported.

**The secondary objective:** differential treatment quality of life trade-offs will be prospectively and systematically assessed using both validated “traditional” and “non-traditional” patient reported outcome measures (PRO). 4 “Traditional” PRO will measure disability related to voice (VHI-10^1), swallowing (EAT-10^2), breathing (COPD dyspnea), and global quality of life (SF-12) (IR4). 4 “Non-traditional” PROs focused on 1) social support, participatory decision-making style, disease anxiety and burden and fear of disease recurrence will also be administered at the initial visit. Responses to PROs tend to change in chronic disease states since severity of the measured concept is time-variable. This is particularly true for iSGS patients whose symptoms markedly improve after treatment and revert and worsen before subsequent treatments. To better understand the breadth of patient experience with this condition, PROs will employed at a priori determined intervals after diagnosis and treatment, (e.g. immediately pre-intervention, 3, 6, and 12, post-intervention), to obtain a more accurate portrait of the survivorship experience related to the different therapeutic modalities.

**Data analysis plan for secondary endpoints:** The secondary objective of this study is to evaluate the quality of life (QOL) scores, e.g., SF12, Dyspnea index, EAT-10, and VHI10, among three study groups. The 95% confidence interval (CI) method based on the Normal distribution will be applied to estimate the quality of life score among three study groups. The mixed effect model will be applied to exam the correlation between the quality of life score and the study groups.

The strategy to be used for developing the multivariable models for QOL involves the following steps: (1) Apply multiple imputation for missing covariate values to make good use of partial information. (2) Choose an appropriate statistical model based on the nature of the response variable.

(3) Decide on the allowable complexity of the model (i.e., the number of covariates) based on the effective sample size available. (4) Allow for nonlinear predictor effects using regression splines. (5) Incorporate pre-specified interactions. (6) Check distributional assumptions. (7) Adjust the variance-covariance matrix for multiple imputation. (8) Quantify the clinical utility (discrimination ability) of the model. (9) Internally validate the calibration and discrimination of the model using the bootstrap approach, e.g., .632+ bootstrap, to estimate the model's likely performance on a new set of subjects. The statistical analyses will be completed by either R 3.1.1 or SAS 9.4 statistical program in this project

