The proposed prospective study (NoAAC PR-02) is designed to fill this void, and leverages and builds upon our previous retrospective multi-institutional investigation, the North American Airway Collaborative RP-01 (NoAAC RP-01). In that study nearly 500 iSGS patients were identified and followed from ten expert tertiary care centers. Specifically, the need for repeat surgery, frequency of disease recurrence, and need for tracheostomy were identified as primary outcome measures.

Collaboration of experienced high volume centers in both the United States and the United Kingdom provided us with the largest and most representative signature of this disease’s epidemiology, natural history, and current management. Inclusion of patients across region and national borders ensured a racially/ethnically representative cohort spanning a range that includes socioeconomic disadvantaged and medically underserved patients. Interestingly, this condition was shown to be quite similar at the separate centers; as it nearly universally affects 40 – 60 year old women (median age 50.3, 95% CI 49.1 – 51.5) who undergo a median 1.75 surgeries per year (95% CI 0.8 – 2.6) (Figure 3). The NoAAC RP-01 study also found variation in the standard of care for iSGS at expert centers. Three basic treatment approaches were used (i.e. endoscopic dilation, endoscopic resection with adjuvant medical therapy, and open anterior neck surgery) despite an absence of randomized controlled trials (RCTs) or other rigorous comparative studies to assess their differential effectiveness at avoiding disease recurrence or tracheostomy.

**Figure 3.** Recurrent nature of interventions in iSGS. Operative procedure number vs. recurrence interval. Each line represents individual patient.

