## 4.0 Randomization

There is no randomization as part of this study. This is a prospective observational multicenter study consisting of approximately 30 centers (Appendix 1). Each center enrolling patients will utilize a common diagnostic algorithm (Appendix 2), and then apply their explicitly defined standard of care. The patients will be prospectively tracked for outcomes with respect to disease recurrence, need for

additional surgery, tracheostomy, as well as subjective patient reported outcomes in breathing, voice, and swallowing.

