**Protocol.** Once enrolled and consented, patients will receive standard of care treatment at the respective center (Appendix 1) and will be followed longitudinally for symptom changes, need for further treatment, complications, and will have PROs (Appendix 2) administered at *a priori* determined intervals.

**Data collection:** *Data collection for the proposed clinical cohort study will include the following case report forms (CRFs) (Appendix 3), implemented in an electronic data capture (EDC) system (please see further details, below, regarding EDC development and implementation).*

- Baseline. Baseline data will include such things as demographics, medical and surgical history, physical exam findings, and relevant diagnostics
- Procedure. Details of initial surgical procedure will be captured (e.g. site and degree of narrowing within the trachea). This information along with other procedure related information will be abstracted from the operative procedure note and clinical record into the EDC.
- Recurrence. At patient recurrence, information regarding the date of recurrence will be captured as for the initial procedure.
- Patient-reported outcomes (PROs). Validated PRO instruments will be utilized to assess patient quality of life. These relate to voice (VHI-10), dysphagia (EAT-10), breathing (COPD dyspnea), and general quality of life (SF-12). Additionally 4 “Non-traditional” PROs focused on 1) social support, participatory decision-making style, disease anxiety and burden and fear of disease recurrence will also be administered at the initial visit. Patients will be asked to complete “traditional” and “non-traditional PROs at baseline. The “traditional” PROs will be repeated at recurrence, and at routine intervals post-procedure (e.g., at 3, 6, and 12 months). For patients with Internet access and email connectivity, interval PRO completion may be done directly by the patient into the web-based data capture instrument, with automated email reminders to patients at each PRO interval. For patients without Internet/email access, completion of PROs will be via mailed or in person paper forms, or over the phone with a member of the research team; the research staff will then will transfer PRO data from paper to the EDC.

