#### **12.0 Statistical Considerations**

##### **Study Hypotheses**

1. There is variation in Time to Recurrence (TTR) between centers using similar surgical approaches for iSGS
2. There is variation in TTR between centers using different surgical approaches for iSGS.
3. The different surgical approaches are associated with unique tradeoffs in terms of voice, swallowing, breathing, and global quality of life.

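### Hypothesis 1 (variation in time to recurrence between centres using the same approach) has no stated analysis, and the between-group tests and Cox model state no handling of centre

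*Combined protocol and SAP*

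**What the plan says.** Under Study Hypotheses (Section 12.0), Hypothesis 1 reads "There is variation in Time to Recurrence (TTR) between centers using similar surgical approaches for iSGS". Hypothesis 2 is also worded at centre level, for centres using different approaches.

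On how treatment is set, Section 4.0 says "Each center enrolling patients will utilize a common diagnostic algorithm (Appendix 2), and then apply their explicitly defined standard of care", and Section 5.0 (Protocol) repeats that patients get the standard care of their centre. On the earlier retrospective study, Section 1.0 reports "The NoAAC RP-01 study also found variation in the standard of care for iSGS at expert centers". It also says of the disease itself that "this condition was shown to be quite similar at the separate centers".

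The Final Analysis Plan defines the primary analysis as estimation: "For the primary objective analysis, i.e., estimating the TTR with 95% confidence interval, the TTR time will be estimated using the Kaplan-Meier method". For group comparison it adds "The logrank test will be used to compare the equality of survival curves", with generalized Wilcoxon and log-likelihood tests alongside. On modelling it says "The Cox proportional hazards model will be applied to investigate potential prognostic factors, such as age on the TTR data".

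The confounding strategy in Section 12.0 adds geographic location, provider characteristics (training, procedural volume, criteria for open surgery) and an interaction of age with facility region. It also plans an instrumental-variable analysis, based on distance to the treating facility, for unobserved confounding. A mixed model appears only for quality of life, and its random effects are not named.

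**The concern.** There are two gaps.

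The first needs no assumption. Hypothesis 1 concerns variation between centres within an approach. Answering it requires centre identity in a TTR analysis, and none is described.

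The second is conditional. If treatment follows centre and centres differ in recurrence for other reasons, patients within a centre are not independent replicates for the treatment comparison. A logrank test or Cox model that treats them as independent then understates the uncertainty, so a difference between centres can be reported as a difference between treatments with too small a p-value and too narrow an interval. The plan's own text makes both conditions plausible: care follows the centre, and Hypothesis 1 expects centres to differ. If approaches are mixed within centres, the second gap largely disappears and the first remains.

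**Working it through.** **1. The plan's precision figures.** Sample Size Considerations gives half-widths below .24 (about 100 patients) and below .13 (about 800). The worst-case binomial half-width, 1.96 × √(0.25/n), is 0.098 at n = 100 and 0.035 at n = 800. Both meet the bounds but do not reproduce them: .24 and .13 correspond to effective sizes of (1.96/.24)² × 0.25 = 16.7 and (1.96/.13)² × 0.25 = 56.8, which the documents do not explain. Clustering does not break the bounds over a wide assumed range. With 30 equal centres, m = 1100/30 = 36.7. At an assumed intraclass correlation of 0.10 the design effect is 1 + 35.7 × 0.10 = 4.57, giving 0.098 × √4.57 = 0.209 and 0.0346 × √4.57 = 0.074. The issue therefore lies in the between-group comparison.

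**2. Inputs for the comparison.** From the documents: dilation about 800 and open surgery about 100. Assumed: no treatment effect; recurrence at 1.75 per year (Section 1.0's median number of surgeries per year, used as a rate); censoring uniform over 36–60 months; normal centre effects on the log-hazard with SD σ = 0.1, 0.2 or 0.3. Section 1.0's remark on similarity across centres favours the low end. Neither σ nor the treatment-by-centre mix is in the supplied text. The layouts below (36 centres averaging 25 patients) are illustrations. The protocol itself gives about 30, 40 and 45 sites in different places.

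**3. Formula.** At this rate almost everyone recurs before censoring (exp(−1.75 × 3) = 0.005 event-free at 36 months). The independent-patient variance of the log hazard ratio is therefore about V₀ = 1/100 + 1/800 = 0.01125. With o open and d dilation patients in a centre, centre effects add σ²Q, where Q = Σ(o/100 − d/800)². The true variance is 1 + σ²Q/V₀ times the assumed one, and the error at nominal 5% is 2[1 − Φ(1.96/√(1 + σ²Q/V₀))].

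- Mixed within centres (28 centres with 22 dilation and 3 open; 8 with 23 and 2): Q = 28 × 0.0025² + 8 × 0.00875² = 0.0008. Inflation is at most 1.006.
- A few centres do most open surgery (4 with 5 and 20; 20 with 24 and 1; 12 with 25 and 0): Q = 4 × 0.19375² + 20 × 0.02² + 12 × 0.03125² = 0.170. Inflation is 1.15 / 1.60 / 2.36.
- Fixed by centre (32 dilation and 4 open centres of 25): Q = 4 × 0.25² + 32 × 0.03125² = 0.28125. Inflation is 1 + 25σ² = 1.25 / 2.00 / 3.25.

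**4. Results.** Two-group logrank error at nominal 5%:

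| Layout | Formula, σ = 0.1 / 0.2 / 0.3 | Simulation (4000 replicates) |
|---|---|---|
| Mixed within centres | 5.0 / 5.0 / 5.1% | 5.1 / 4.6 / 4.2% |
| A few centres do most open surgery | 6.8 / 12.2 / 20.2% | 6.3 / 11.0 / 18.3% |
| Fixed by equal centres | 8.0 / 16.6 / 27.7% | 8.2 / 15.7 / 25.8% |

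A separate simulation of the three-group logrank test (80/10/10 split, about 1000 patients) gave 5–6% when mixed. When fixed by centre it gave 9.9 / 22 / 39% with 30 centres and 8.1 / 18 / 30% with 40.

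**5. Does any other analysis close the gaps?** The provider and region terms are measured characteristics, not centre identity. They belong to the propensity and multivariate model, not to the tests in the Final Analysis Plan. The instrumental-variable analysis targets bias from unmeasured factors and states no clustered variance. None of these estimates between-centre variance in TTR.

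**The case against.** The strongest reply is that the primary analysis is Kaplan-Meier estimation, the study is sized on interval width, and no alpha or power is stated. That stands: the logrank, Wilcoxon and Cox analyses are supporting comparisons. A reader might infer that the primary estimates or the sample size justification fail. The documents do not support this, because the Kaplan-Meier intervals are adequate for the enrolled centres and the half-width bounds hold in step 1.

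A second reply is that the plan has tools for this. The Cox covariate list is open, provider and region covariates are listed, and an instrument is planned for unobserved confounding. This also stands as partial mitigation. It would be wrong to say that centre will be left out or that unmeasured centre differences are ignored. An open list is not pre-specification, however, and none of these tools supplies centre-level variance or answers Hypothesis 1. Procedural volume and region may explain some centre variation but do not measure it.

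A third reply is that the size is wholly assumed. It is. Appendix 1 is not in the supplied text, and the confounding section implies some patient-level choice of treatment. Much higher error can be produced: 15 / 35 / 51% with a dilation-only lead site of 700 and four open-only centres. A reader might infer this from the lead site's target of 750–800 recruits. No section says that those patients are treated there or receive only dilation, and phone and electronic consent are allowed. With a lead site that mixes treatments, the error is 5–6%.

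**Conclusion.** The omission is established by the text, with high confidence: Hypothesis 1 has no analysis, and the between-group TTR tests and Cox model state no handling of centre. Confidence in the size of the harm is low. It depends on two quantities that the documents do not give, the treatment-by-centre mix and the centre SD. For an SD of 0.1–0.3, the two-group logrank error is about 5% if treatments are mixed, about 6–18% if a few centres do most open surgery, and about 8–26% if treatment is fixed by equal centres. It is higher only if one large site also dominates while treatment follows centre. The plan should be amended. The gap does not invalidate the primary estimates.

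**What to change.** 1. For the treatment comparison, fit the Cox model with treating centre (not recruiting site) as a shared frailty, estimated by REML. Take the hazard ratio and interval with a pre-specified small-cluster t reference, for example df = centres minus treatment groups, reduced further for any centre-level covariates. Keep the unadjusted logrank test as descriptive. In simulation without covariates, a t reference with df = centres minus 2 gave 1.4–7.7% error over all layouts tried. The Wald z reached 10.5% with the dominant dilation-only site and four open centres.
2. Report the between-centre variance in TTR within each approach, with its confidence interval, as the analysis of Hypothesis 1.
3. Tabulate treatment by centre, and report a centre-stratified comparison where centres offer more than one approach. State that where treatment is fixed by centre, frailty widens the interval but cannot separate treatment from centre: a systematic 0.2 log-hazard difference of open-surgery centres would still appear as a hazard ratio of exp(0.2) = 1.22.

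**Cost.** SAP wording only, since the treating facility is already needed for the distance instrument. The price is wider intervals where treatment follows centre. Multiplying the simulated SE ratios by t/1.96 gives:

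- Mixed across 36 centres: at most 1.01 × 2.032/1.96 = 1.05 times.
- Fixed by equal centres (df 34): 1.10 / 1.38 / 1.79 × 1.037 = 1.14 / 1.43 / 1.86 times.
- Dominant dilation-only site with four open centres (9 centres, df 7): 1.17 / 1.61 / 2.16 × 2.365/1.96 = 1.41 / 1.94 / 2.61 times.

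Centre-level covariates would widen these further. The answer to Hypothesis 1 may also be imprecise. At a true SD of 0.2, 95% of simulated dilation-group estimates fell in 0.04–0.30 with 32 centres of 25, and in 0.01–0.38 with a 700-patient site and four others.

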**Strategy to address confounding by selection bias:** Observational studies (like our proposed investigation) that lack randomization of subjects into treatment groups and must address selection bias to properly estimate the effect of treatment. We will apply a propensity scoring method (PSM) and instrumental variable (IV) method to adjust for observed and unobserved confounding, respectively. Propensity scoring will be used to mitigate the expected biases from observed confounding in the proposed observational study. It is a balancing score that effectively makes the distribution of measured baseline covariates similar between treatment groups. This is important because the apparent difference in outcome between those treated with endoscopic dilation versus those treated with endoscopic resection or open anterior neck surgery may depend on characteristics that affected whether or not a patient received a given treatment instead of due to the actual effect of the treatment. This issue is relevant to our study Aims #2 and #3, but for illustrative purposes, the specific analytic approach will be described in the context of Aim #2. Its objective is to determine factors that affect time to stenosis recurrence in patients with idiopathic subglottic stenosis. In this analysis, the dependent variable is time to recurrence and the primary independent variable is treatment type: endoscopic dilation versus endoscopic excision or open anterior neck surgery of the affected portion of the trachea.

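### No treatment comparison of time to recurrence is specified as both adjusted for selection and suited to censored data, and none is designated primary

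*Combined protocol and SAP*

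**What the plan says.** Section 4.0 states the design: "There is no randomization as part of this study". Each center applies its own standard of care.

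Section 12.0, Final Analysis Plan, sets the objective: "The primary objective of this study is to evaluate the time to recurrence (TTR) among three possible treatment groups". The paragraph on the primary endpoint then contains three layers:

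- **Estimation.** "For the primary objective analysis, i.e., estimating the TTR with 95% confidence interval", by Kaplan-Meier with several types of interval and band.
- **Tests.** "The logrank test will be used to compare the equality of survival curves". In addition, "The generalized Wilcoxon and log-likelihood tests will also be examined". No weighting, stratification or covariate is mentioned for any of the three.
- **Cox model.** "The Cox proportional hazards model will be applied to investigate potential prognostic factors, such as age on the TTR data". The paragraph ends its account of that model with "The adjusted hazard ratios and 95% CIs will be reported". It gives no covariate list and does not say that treatment group is in the model.

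The later part of Section 12.0 on confounding by selection bias says that observational studies such as this one "lack randomization of subjects into treatment groups and must address selection bias to properly estimate the effect of treatment". For TTR by treatment type it plans propensity scoring (stratification, then regression), multivariate regression for residual imbalance, and an instrumental variable based on distance to the treating facility. It gives a long list of covariates. It calls TTR a continuous variable and defines the propensity effect as a difference in mean time.

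**The concern.** Aim II is a comparison of treatments, and the results are meant to help patients choose between them. Treatment here follows center practice and patient characteristics. The covariate list even includes each provider's criteria for open surgery, so the plan itself expects the groups to differ at baseline.

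An unadjusted survival test in that setting mixes the effect of treatment with the effect of who received it. The plan's remedy is in a separate part of Section 12.0 and uses a different effect measure, one that does not say what happens to patients without a recurrence by the end of follow-up. If the unadjusted survival result and the adjusted mean-time result disagree, nothing in the plan says which one answers the primary question. That choice would be open after the data are seen.

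**Working it through.** **Plan's own figure.** There is none for this comparison. The sample size section rests on confidence-interval half-widths and gives no power, effect size or test level, so there is no figure to reproduce.

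**Step 1: the specified analyses of TTR by treatment, side by side.**

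| Analysis (Section 12.0) | Allows for censoring? | Adjusted for selection? | Treatment is the exposure? |
|---|---|---|---|
| Kaplan-Meier curves | Yes | Not stated | Yes, by group |
| Logrank, Wilcoxon, log-likelihood tests | Yes | Not stated | Yes |
| Cox model | Yes | Adjusted, covariates not listed | Not stated |
| Propensity analysis | Not stated; difference in mean time | Yes | Yes |
| Instrumental variable, two-stage | Not stated | Yes | Yes |

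No row is explicitly affirmative in all three columns, and no row is marked as the primary comparison.

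**Step 2: what an unadjusted test could do.** Every input except the group sizes is an assumption. The group sizes are the plan's approximate 800 dilation, 100 resection and 100 open surgery. There is no true treatment effect. Times are exponential with baseline rate 0.5 per year, censoring is uniform between 1 and 5 years, and there is one binary confounder with 50% prevalence in dilation and resection. Each setting has 1,000 runs of the three-group logrank test at nominal 0.05. The simulation standard error at 5% is √(0.05 × 0.95 / 1000) = 0.007.

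| Confounder hazard ratio | Prevalence in open surgery | Unadjusted rejection | Stratified on confounder |
|---|---|---|---|
| 1.5 | 40% / 30% / 20% | 0.052 / 0.072 / 0.127 | 0.050 / 0.052 / 0.062 |
| 2.0 | 40% / 30% / 20% | 0.071 / 0.149 / 0.287 | 0.043 / 0.048 / 0.047 |
| 3.0 | 40% / 30% / 20% | 0.105 / 0.295 / 0.528 | 0.054 / 0.057 / 0.046 |

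With equal prevalence (50% in all groups), both tests reject in 0.05 to 0.06 of runs.

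A second, two-group simulation used 800 against 100, a rate of 1.0 per year, censoring at 3 years and 1,000 runs. With a confounder hazard ratio of 1.3 per SD and imbalance of 0.2, 0.4 and 0.6 SD, rejection was 6.8%, 14.1% and 25.1%. With a hazard ratio of 1.5 per SD it was 9.3%, 23.5% and 49.1%.

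**Step 3: why a plain mean difference does not fit censored times.** Take two groups with the event rates used above, λ = 0.5 and 1.0 per year, both censored at C = 3 years. True mean times are 1/λ = 2.00 and 1.00 years, a difference of 1.00 year.

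- Censored times counted as recurrence times: the mean is (1 − e^(−λC))/λ. This gives (1 − 0.2231)/0.5 = 1.554 and (1 − 0.0498)/1.0 = 0.950, a difference of 0.60 year.
- Censored patients dropped: the mean is [1 − e^(−λC)(1 + λC)] / [λ(1 − e^(−λC))]. This gives 1.138 and 0.843, a difference of 0.30 year.

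The same truth gives 0.60 or 0.30 instead of 1.00, depending on a rule that the plan does not state.

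**The case against.** The strongest reply is that Section 12.0 must be read as a whole. It recognises selection bias and plans propensity stratification, regression and an instrumental variable for this same endpoint and exposure, with covariates listed in advance. Unadjusted Kaplan-Meier curves with a logrank test are normal first-stage reporting in a cohort. This stands: a reader might infer that the plan ignores confounding, and the documents do not support that.

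Two other strong readings also fail. A reader might take the logrank test as the only between-group test, but the same paragraph names two more, equally unadjusted. A reader might call it the headline comparison, but the paragraph labels estimation as the primary objective analysis, and nothing ranks the logrank test above the adjusted analyses.

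It is also fair to say that the Cox model could contain treatment, since age is given only as an example and adjusted hazard ratios are promised. This is an ambiguity and does not show that treatment is left out. Likewise, the mean difference could be computed as a restricted mean that allows for censoring. In both cases the plan does not say so.

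Finally, the simulations rest on assumed inputs and show a general property of unadjusted tests. They do not measure bias in this study.

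The reply does not remove the gap in the table: no comparison is specified as both adjusted and suited to censored data, and no order of precedence is given.

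**Conclusion.** The point holds as a gap in specification. The tests named for the primary endpoint are unadjusted, the Cox model is not stated to contain treatment, and the adjusted analysis uses an effect measure with no stated handling of censoring. No analysis is designated as the primary treatment comparison.

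The size of any bias cannot be computed from the documents. On assumed confounding, false-positive rates run from about 5%, where imbalance or confounder strength is small, to about 50%, where both are large. That range shows what is at risk and should not be quoted as an estimate for this cohort. The mean-time illustration also rests on assumed event rates and follow-up.

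This should be fixed before the analysis. It is not a fatal flaw, because the adjustment methods and covariates are already in the plan and mainly need to be linked to the survival analysis.

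**What to change.** In the primary endpoint paragraph of the Final Analysis Plan:

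1. Designate as the primary between-group comparison a Cox model with the three-level treatment group as the exposure, stratified on the propensity score and adjusted for the covariates already listed in Section 12.0. Report the three pairwise adjusted hazard ratios with 95% confidence intervals.
2. State that the score comes from a multinomial model or from pairwise models. The plan's logistic regression of treatment status does not say how three groups are handled.
3. Label the unadjusted Kaplan-Meier curves and the logrank, Wilcoxon and log-likelihood tests as descriptive.

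In the selection-bias part, replace the mean-time difference with this contrast.

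Stratification plus regression is the approach the plan already chose. Propensity weighting would be an alternative, but preferring it is a matter of taste.

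**Cost.** This is a change of wording that uses covariates already planned for collection. Intervals will be wider. Overlap may be limited: with the five strata that the plan mentions, a group of about 100 averages 100/5 = 20 patients per stratum, and some strata may hold far fewer where center practice largely determines treatment. Overlap should be checked and reported for each pair of treatments.
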